### **8.1 Accrual Estimates**

A total of 16 patients are going to be enrolled. Estimated accrual is 2-3 per month. Projected completion of accrual from the activation of the study is 9 months and last patient follow-up will be completed in 12 months from the activation.

## 8.2 Sample Size Considerations

This is a phase II study that aims to obtain preliminary evidence of feasibility. The proposed sample of n=16 would allow estimating the rates with margins of error of 0.345 at 95% confidence level.

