### 3.2 Sample Size

Target accrual is a total of 16 patients, and to account for screen failures and withdrawals, we will consent up to 18 patients. Patients can be enrolled to the and can get concurrent chemoradiation with weekly cisplatin (40 mg/m^2) given once a week or concurrent chemoradiation with high dose cisplatin (80-100 mg/m^2) given every 3 weeks. Participants who do not receive any dose of STS will not be evaluable and will be replaced.

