## **8 Statistical Considerations and Analysis Plan**

Feasibility will be evaluated as the successful completion of 5 weekly cisplatin or 2 every-3-week cisplatin without any extended treatment related delays more than 7 days by at least 75% of patients. Safety will be measured by:

- Frequency of drug related adverse events occurring up to 7 days after the last dose of STS
- Frequency of serious adverse events occurring up to 7 days after the last dose of STS
- Frequency of clinical laboratory test abnormalities by worst toxicity grade using NCI CTCAE version 5.0

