## 8.4 Analyses Plans

We will report the proportion of patients experiencing high-grade toxicity with exact binomial 95% confidence intervals. We will also describe patient experiences with respect to feasibility as defined above. All other adverse events will be similarly summarized by type and grade.

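### The 95% margin of error of 0.345 in section 8.2 is not attainable with 16 patients (the maximum is about 0.25), and section 8.4 names no interval for the primary feasibility proportion

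*Combined protocol and SAP*

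**What the plan says.** Section 8.2 describes the study as seeking preliminary evidence of feasibility and then gives its whole sample-size argument: "The proposed sample of n=16 would allow estimating the rates with margins of error of 0.345 at 95% confidence level". It names neither the assumed rate nor the interval method, and it does not say whether the level is one- or two-sided.

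The sample of 16 is the total. Section 8.1 says "A total of 16 patients are going to be enrolled", and section 3.2 says "Target accrual is a total of 16 patients, and to account for screen failures and withdrawals, we will consent up to 18 patients". Both cisplatin regimens fall within that one total, and no number per regimen is set.

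The primary endpoint (section 2.2) is completion of a minimum number of cisplatin doses without a long treatment-related delay. The opening of section 8 judges it as completion "without any extended treatment related delays more than 7 days by at least 75% of patients".

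For the analysis, section 8.4 says: "We will report the proportion of patients experiencing high-grade toxicity with exact binomial 95% confidence intervals". On the primary endpoint it says only: "We will also describe patient experiences with respect to feasibility as defined above". The sentence after that, "All other adverse events will be similarly summarized by type and grade", extends the toxicity summary to other adverse events and does not reach feasibility.

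**The concern.** A margin of error for a single proportion is largest when the true rate is 50%. For 16 patients that worst case is close to one quarter, so 0.345 looks wrong on sight. The plan contains no power calculation, null rate or other precision statement. If this figure fails, nothing quantitative in the document supports the choice of 16.

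The second matter concerns the primary result itself. The feasibility criterion is a point estimate compared with 75%. In a sample this small such a comparison says little without an interval, and section 8.4 promises an interval for toxicity but not for feasibility. Section 1.3 says a larger study could follow if feasibility and safety look promising, so readers of the result will need to see how uncertain it is.

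**Working it through.** **Inputs.** n = 16 and 95% confidence (section 8.2); 75% criterion (section 8); exact binomial intervals (section 8.4, for toxicity). Two-sided intervals are assumed. A one-sided 95% margin would be smaller: 0.206 by the normal approximation.

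**Trying to reproduce 0.345 at n = 16**

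- Normal approximation: 1.96 × √(p(1−p)/n). At p = 0.5 this is 1.96 × √(0.25/16) = 1.96 × 0.125 = **0.245**. At p = 0.75 it is 1.96 × √(0.1875/16) = 0.212.
- Exact (Clopper-Pearson): for x successes the limits are the 2.5% quantile of Beta(x, n−x+1) and the 97.5% quantile of Beta(x+1, n−x). The widest interval is at 8/16, from 0.2465 to 0.7535, so the half-width is (0.7535 − 0.2465)/2 = **0.2535**. Exact intervals are asymmetric. The longest distance from estimate to limit, over all x, is 0.274 (at 5/16 or 11/16).

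| 95% method, n = 16 | Largest half-width | Longest arm |
|---|---|---|
| Normal | 0.245 | 0.245 |
| Normal, continuity-corrected (0.245 + 0.5/16) | 0.276 | 0.276 |
| Exact (Clopper-Pearson) | 0.2535 | 0.274 |
| Wilson | 0.220 | 0.245 |
| Agresti-Coull | 0.220 | 0.2505 |
| Jeffreys | 0.228 | 0.243 |

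Replacing 1.96 by a t quantile gives 0.266 to 0.275. None of these reaches 0.345.

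**Changing an input**

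- Using the 18 patients who may be consented gives smaller margins: 0.231 (normal) and 0.240 (exact).
- Raising the confidence level at n = 16 gives 0.322 (normal) or 0.310 (exact) at 99%, and 0.351 or 0.330 at 99.5%. Equivalently, 0.345/0.125 = 2.76 standard errors, which is about 99.4% two-sided confidence.
- Solving the normal formula for n gives (1.96 × 0.5/0.345)² = 8.07. At n = 8 the maximum is 0.3465 (normal) or 0.343 (exact; 4/8 gives 0.157 to 0.843). This is close to 0.345, but neither value rounds to it.

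**Size of the discrepancy.** 0.345 − 0.245 = 0.100; 0.345 − 0.2535 ≈ 0.092.

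**What an interval for feasibility would show.** Exact 95% intervals at n = 16:

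| Feasible | Proportion | Exact 95% CI |
|---|---|---|
| 12/16 | 75.0% | 47.6% to 92.7% |
| 14/16 | 87.5% | 61.7% to 98.4% |
| 15/16 | 93.75% | 69.8% to 99.8% |
| 16/16 | 100% | 79.4% to 100% |

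The criterion is met from 12/16 upwards, but only 16/16 has a lower limit above 75%.

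**The case against.** The consequence of the number is small. No success criterion, stopping boundary or analysis uses 0.345, section 8.2 claims only preliminary evidence, and n = 16 was not derived from a target precision. If the figure is meant for 16 patients, it understates precision, which is the safe direction. All of this stands, and it limits the weight of the point.

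The figure may also have been meant per regimen. Section 2.3 reports secondary endpoints by cohort, section 5.4 applies the stopping rule within each cisplatin stratum, and about 8 patients would give roughly 0.345. In that case the fault would be a mislabelled n rather than a wrong margin. The reading is plausible but unproven: the sentence names 16, no section sets 8 per regimen, and neither the normal nor the exact value at n = 8 matches. Either way the sentence cannot stand as written.

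On the interval, section 8.2 speaks of estimating rates at 95% confidence in a paragraph about feasibility, so some interval was probably intended, and any reader can compute one from the counts. That is fair. What is missing is the commitment in section 8.4 and the named method. Standing alone, this would be a missing detail in reporting rather than an error.

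**Conclusion.** The margin in section 8.2 is wrong for the sample it names. At n = 16 and two-sided 95% confidence the maximum is 0.245 (normal) or 0.253 (exact half-width), against 0.345 stated. The conclusion does not depend on the choice of method, since every 95% margin computed is at most 0.276. Where 0.345 came from cannot be settled from the documents. Because it is the plan's only quantitative support for its sample size, it should be corrected. It does not alter the design, the stopping rule or the number of patients.

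The absence of a named interval for the primary feasibility proportion is a secondary point, but it has more bearing on how the result is read. A result that just meets the criterion, 12/16, is compatible with true rates from 47.6% to 92.7%.

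**What to change.** In section 8.2, state which n, rate and method 0.345 refers to. If it was meant for all 16 patients, replace it with a maximum 95% margin of 0.245 (normal approximation) or about 0.25 (exact half-width, which fits the method in section 8.4). If it was meant per regimen, give that sample size and add the margin for 16.

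In section 8.4, add that the primary feasibility proportion will be reported with the exact binomial 95% confidence interval already planned for high-grade toxicity, alongside the comparison with 75%.

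The cost is one corrected or explained number and one added sentence. No patients, data or procedures change.

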## 8.3 Interim Analyses and Stopping Rules

There is no plan for interim analyses in this phase II study. Stopping rules are illustrated in section 5.3.

## 8.4 Analyses Plans

We will report the proportion of patients experiencing high-grade toxicity with exact binomial 95% confidence intervals. We will also describe patient experiences with respect to feasibility as defined above. All other adverse events will be similarly summarized by type and grade.

# 9 Study Management

## 9.1 Pre-study Documentation

This study will be conducted in accordance with the ethical principles that have their origin in the Declaration of Helsinki as stated in 21 CFR §312.120(c)(4); consistent with GCP and all applicable regulatory requirements.

Before initiating this trial, the PI will have written and dated approval from the Institutional Review Board for the protocol, written informed consent form, subject recruitment materials, and any other written information to be provided to participants before any protocol related procedures are performed on any participants.

The PI must comply with the applicable regulations in Title 21 of the Code of Federal Regulations (21 CFR §50, §54, and §312), GCP/ICH guidelines, and all applicable regulatory requirements. The IRB must comply with the regulations in 21 CFR §56 and applicable regulatory requirements.

The clinical investigation will not begin until either FDA has determined that the study under the Investigational Drug Application (IND) is allowed to proceed or the FDA has determined that the study is exempt from IND requirements.

## 9.2 Institutional Review Board Approval

The protocol, the proposed informed consent form, and all forms of participant-facing materials related to the study (e.g. advertisements used to recruit participants) will be reviewed and approved by the UCSF IRB. Prior to obtaining IRB approval, the protocol must be approved by the Helen Diller Family Comprehensive Cancer Center Site Committee and by the Protocol Review Committee (PRC). The initial protocol and all protocol amendments must be approved by the IRB prior to implementation.

## 9.3 Informed Consent

All participants must be provided a consent form describing the study with sufficient information for each participant to make an informed decision regarding their participation. Participants must sign the IRB -approved informed consent form prior to participation in any study specific

procedure. The participant must receive a copy of the signed and dated consent document. The original signed copy of the consent document must be retained in the medical record or research file.

#### **9.4 Changes in the Protocol**

Once the protocol has been approved by the UCSF IRB, any changes to the protocol must be documented in the form of an amendment. The amendment must be signed by the PI and approved by PRC and the IRB prior to implementation.

If it becomes necessary to alter the protocol to eliminate an immediate hazard to participants, an amendment may be implemented prior to IRB approval. In this circumstance, however, the PI must then notify the IRB according to institutional requirements.

#### **9.5 Handling and Documentation of Clinical Supplies**

The PI will maintain complete records showing the receipt, dispensation, return, or other disposition of all investigational drugs at the site. The date, quantity and batch or code number of the drug, and the identification of participants to whom the investigational product has been dispensed by participant number and initials will be included.

The PI shall not make the investigational drug available to any individuals other than to qualified study participants. Furthermore, the PI will not allow the investigational product to be used in any manner other than that specified in this protocol.

#### **9.6 Case Report Forms (CRFs)**

The PI and/or designee will prepare and maintain adequate and accurate participant case histories with observations and data pertinent to the study. Study specific Case Report Forms (CRFs) will document safety and treatment outcomes for safety monitoring and data analysis. All study data will be entered into OnCore® via standardized CRFs in accordance with the CTMS study calendar, using single data entry with a secure access account. Study personnel will complete the CRFs; the PI will review and approve the completed CRFs.

The information collected on CRFs shall be identical to that appearing in original source documents. Source documents will be found in the participant's medical records maintained by study personnel. All source documentation should be kept in separate research files for each participant.

In accordance with federal regulations, the PI is responsible for the accuracy and authenticity of all clinical and laboratory data entered onto CRFs. The PI will approve all completed CRFs to attest that the information contained on the CRFs is true and accurate.

The PI will be responsible for ensuring the accurate capture of study data. At study completion, when the CRFs have been declared to be complete and accurate, the database will be locked. Any changes to the data entered into the CRFs after that time can only be made by joint written agreement among the PI and the trial statistician.

All source documentation and CTMS data will be available for review/monitoring by the UCSF DSMC and regulatory agencies.

#### **9.7 Oversight and Monitoring Plan**

The UCSF Helen Diller Family Comprehensive Cancer Center DSMC will be the monitoring entity for this study. The UCSF DSMC will monitor the study in accordance with the NCI-

approved Data and Safety Monitoring Plan (DSMP). The DSMC will routinely review all adverse events and suspected adverse reactions considered “serious”. The DSMC will audit study-related activities to ensure that the study is conducted in accordance with the protocol, local standard operating procedures, FDA regulations, and Good Clinical Practice (GCP). Significant results of the DSMC audit will be communicated to the IRB and the appropriate regulatory authorities at the time of continuing review, or in an expedited fashion, as applicable. See Appendix 2 - Data and Safety Monitoring Plan.

## 9.8 Record Keeping and Record Retention

The PI is required to maintain adequate records of the disposition of the drug, including dates, quantity, and use by subjects, as well as written records of the disposition of the drug when the study ends.

The PI is required to prepare and maintain adequate and accurate case histories that record all observations and other data pertinent to the investigation on each individual administered the investigational drug or employed as a control in the investigation. Case histories include the case report forms and supporting data including, for example, signed and dated consent forms and medical records including, for example, progress notes of the physician, the individual's hospital chart(s), and the nurses' notes. The case history for each individual shall document that informed consent was obtained prior to participation in the study.

Study documentation includes all CRFs, data correction forms or queries, source documents, Sponsor-Investigator correspondence, monitoring logs/letters, and regulatory documents (e.g., protocol and amendments, IRB correspondence and approval, signed participant consent forms).

Source documents include all recordings of observations or notations of clinical activities and all reports and records necessary for the evaluation and reconstruction of the clinical research study.

In accordance with FDA regulations, the PI shall retain records for a period of 2 years following the date a marketing application is approved for the drug for the indication for which it is being investigated; or, if no application is to be filed or if the application is not approved for such indication, until 2 years after the investigation is discontinued and FDA is notified.

## Appendix 1 Performance Status Criteria

ECOG Performance Status Scale		Karnofsky Performance Scale	
Grade	Descriptions	Percent	Description
0	Normal activity Fully active, able to carry on all pre-disease performance without restriction	100	Normal, no complaints, no evidence of disease
		90	Able to carry on normal activity; minor signs or symptoms of disease
1	Symptoms, but ambulatory Restricted in physically strenuous activity, but ambulatory and able to carry out work of a light or sedentary nature (e.g., light housework, office work)	80	Normal activity with effort; some signs or symptoms of disease
		70	Cares for self, unable to carry on normal activity or to do active work
2	In bed < 50% of the time Ambulatory and capable of all self-care, but unable to carry out any work activities Up and about more than 50% of waking hours	60	Requires occasional assistance, but is able to care for most of his/her needs
		50	Requires considerable assistance and frequent medical care
3	In bed > 50% of the time Capable of only limited self-care, confined to bed or chair more than 50% of waking hours	40	Disabled, requires special care and assistance
		30	Severely disabled, hospitalization indicated Death not imminent
4	100% bedridden Completely disabled Cannot carry on any self-care Totally confined to bed or chair	20	Very sick, hospitalization indicated Death not imminent
		10	Moribund, fatal processes progressing rapidly
5	Dead	0	Dead

## **Appendix 2 Data and Safety Monitoring Plan for Phase II or III Institutional Study**

### **1. Oversight and Monitoring Plan**

The UCSF Helen Diller Family Comprehensive Cancer Center (HDFCCC) Data and Safety Monitoring Committee (DSMC) is responsible for auditing data quality and participant safety for all HDFCCC institutional clinical trials. A summary of DSMC activities for this trial includes:

- Semiannual auditing (depending on trial accrual)
- Review of serious adverse events
- Minimum of biennial regulatory auditing

### **2. Monitoring and Reporting Guidelines**

Investigators will conduct a continuous review of data and participant safety at monthly site committee meetings where the results of each participant's treatment are discussed and documented in the site committee minutes.

All institutional Phase II and III therapeutic trials are audited on a semiannual basis, with all data from twenty percent of the enrolled participants audited by the DSMC Monitor/Auditor. The assigned DSMC Monitor/Auditor will review no more than a total of 10 participant charts during the course of auditing this trial. DSMC Monitor/Auditors will send a follow-up report to the study team within 20 business days after the auditing visit is complete for the PI and the study team to resolve all action items from this report within 20 business days. An abbreviated regulatory review (i.e., reviewing protocol and consent versions, SAEs, PVs, DOA logs, 1572 forms, etc.) will occur at each participant monitoring review; however, a full regulatory review will occur on a biennially basis by the DSMC for regulatory compliance.

Auditing of all enrolled participants in these trials will be complete after 20% of enrolled participants have been audited through five cycles of treatment. However, regulatory reviews of the trial, safety reviews (i.e., Serious Adverse Event (SAE) reviews and Protocol Violation (PV) reviews), and audit/inspection preparation (as applicable) will continue until the trial is closed by the IRB.

### **3. Review and Oversight Requirements**

#### **3.1 Adverse Event Monitoring**

All Grade 3-5 adverse events (AEs), whether or not considered to be expected or unexpected and whether or not considered to be associated with the use of the investigational agent(s) or study procedure, will be entered into OnCore®, UCSF's Clinical Trial Management System.

Adverse events are graded according to the Common Terminology Criteria for Adverse Events (CTCAE) as developed and revised by the Common Therapy Evaluation Program (CTEP) of the National Cancer Institute. Adverse events are further given an assignment of attribution or relationship to investigational agent or study procedure. Attribution categories are:

- **Definite** – The adverse event is clearly related to the investigational agent(s) or study procedure.
- **Probable** – The adverse event is likely related to the investigational agent(s) or study procedure.

- **Possible** – The adverse event may be related to the investigational agent(s) or study procedure.
- **Unrelated** – the adverse event is clearly not related to the investigational agent(s) or study procedure.

All Grade 3-5 adverse events entered into OnCore® will be reviewed on a monthly basis at the Site Committee meetings. The Site Committee will review and discuss the selected toxicity, the toxicity grade, and attribution assignment.

### 3.2 Serious Adverse Event Reporting

By definition, an adverse event is defined as a serious adverse event (SAE) according to the following criteria:

- Death.
- Life-threatening (i.e., results in an immediate risk of death).
- Requires inpatient hospitalization or prolongation of existing hospitalization,
- Permanent or significant disability/incapacity
- Gives rise to a congenital anomaly/birth defect, or cancer, or any experience that suggests a significant hazard, contraindication, side effect, or precaution that may require medical or surgical intervention to prevent one of the outcomes listed above.
- Event occurring in a gene therapy study.
- Event that changes the risk/benefit ratio of a study.
- Any other event the Principal Investigator judges to be serious or which would suggest a significant hazard, contraindication, side effect, or precaution.

Serious adverse event reporting will be in accordance with all IRB regulations. For trials conducted under an investigational new drug (IND) application, the SAE will be reported in accordance with Code of Federal Regulation Title 21 Part 312.32 and will be reported on a Med Watch form.

UCSF IRB website for guidance in reporting serious adverse events:

<https://irb.ucsf.edu/adverse-event>

Med Watch forms and information:

[www.fda.gov/medwatch/getforms.htm](http://www.fda.gov/medwatch/getforms.htm)

All serious adverse events are entered into OnCore®, as well as submitted to the IRB (per IRB guidelines). The SAEs are reviewed and monitored by the Data and Safety Monitoring Committee on an ongoing basis and discussed at DSMC meetings, which take place every six weeks. The date the SAE is sent to all required reporting agencies will be documented in OnCore®.

If the SAE involves a subject death, and is determined to be possibly, probably or definitely related to the investigational drug or any research related procedure, the event must be reported to the DSMC Chair (or Vice Chair) and DSMC Director within one business day.

